2.0 Hypothesis: Children who are allergic to milk can be treated via a supervised program of oral immunotherapy (OIT). Successful treatment will be indicated by the ability to ingest dairy products daily with no adverse symptoms. This will be accompanied by a decrease in specific IgE to milk, an increase in IgA and IgG4 blocking antibodies and by increases in milk-specific Regulatory T-cells (Treg) and Regulatory B-cells (Breg).

2.1 Specific Objectives: 1) To determine the efficacy of Oral immunotherapy (OIT) treatment for children with IgE mediated cow's milk allergy (CMA)

2) To determine the safety of OIT for treatment of children with IgE-mediated CMA

3) To determine if successful OIT for children with CMA is associated with increases in blocking antibodies, including milk specific IgA and IgG4

4) To determine if successful OIT for children with CMA is associated with increases in Treg and/or Breg.

2.2 Rationale: CMA is a very common problem in children with important nutritional impact. Moreover, milk is among the most common foods associated with severe allergic reactions and anaphylaxis, and is extremely difficult to avoid. Treatment of CMA is currently based on strict avoidance, which is difficult to adhere to due to the ubiquitous nature of dietary dairy products. Treatment with oral immunotherapy (OIT) has been performed in the USA and Europe, but there are few rigorous, blinded clinical trials, with adequate controls and outcomes. However, there is no current research into OIT for CMA in Canada, depriving our population of a potential cure for this very common problem. A well defined clinical trial with adequate controls and immunological outcomes is essential for understanding the ideal patients and the safest and most efficacious methodologies, and for dissemination of successful milk specific OIT protocols to practitioners for more general use.

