Through a process of stratified randomization (according to sex), participants will be randomly assigned to one of 2 study groups. The first group will receive active desensitization, and the second group will not receive any treatment but will be followed up regularly (Appendix A Table 2). Desensitization will be offered to the observation groups following the trial, should the outcome be successful in the treatment group.

3.2 Oral challenge test to milk. Prior to initiating desensitization and following treatment, the subjects will undergo a placebo controlled oral challenge to milk. These challenges will determine the level at which the children react and will be the baseline to follow their improvement in oral tolerance following therapy.

Oral challenges will be single blinded and will be performed with fresh cow's milk, with increasing doses taken orally every 10 to 15 minutes up to a total of 150ml of milk (doses of 0.1, 0.3, 1.0, 3.0, 10.0, 30.0, 45ml, 60 mL) ^{(49,82) (83)}. Patients will receive 2 challenges per day, 1 placebo and 1 with the active substance (milk). Nurses in the Medical Day Unit/Center for Investigative Medicine will prepare the food and randomize the placebo challenges. Unless contraindicated, the placebo will be soy or rice-based milk. If the challenge is negative after 150 ml of milk, results will be confirmed by means of open challenge, using 250ml of yogurt or ice cream 1 hour after completion of the blinded portion(29) according to the recommendations of the European Academy of Allergology and Clinical Immunology (5). After completing the challenge, patients will be kept under observation for at least 2 hours. Only objective symptoms will be considered to be indicative of a positive allergic reaction (29). Food challenges will be scored as positive if a single symptom or any of the following objective clinical reactions will be observed: urticaria, angioedema, wheezing, rhinitis, vomiting, diarrhea, protracted abdominal pain, exacerbation of atopic dermatitis, or shock. A single episode of vomiting will not be considered as a positive reaction, while severe and repetitive vomiting will. If the challenge is **negative**, ie, the subject is asymptomatic, he/she will be excluded from the study. Based on our experience, approximately 80% of those subjects ages 6 or greater, with positive history and positive skin tests, approached will fail the oral challenge and thus be eligible.

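### Oral challenges are single blind in an open-label trial, and no scorer masked to the milk/placebo order or to arm is specified

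*Combined protocol and SAP*

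**What the plan says.** Section 3.2 of the combined protocol and SAP sets out the challenge:

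- On blinding: "Oral challenges will be single blinded". Each challenge day has one milk session and one placebo session, the placebo being soy or rice milk unless contraindicated.
- On preparation: "Nurses in the Medical Day Unit/Center for Investigative Medicine will prepare the food and randomize the placebo challenges". The section does not say who scores the sessions or who is left unblinded.
- On volume: milk is given in rising doses "up to a total of 150ml of milk". If that is negative, "results will be confirmed by means of open challenge, using 250ml of yogurt or ice cream".
- On scoring: reactions must be objective, but a single symptom is enough for a positive result. The list includes rhinitis and protracted abdominal pain, and one episode of vomiting is treated differently from severe, repeated vomiting.

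The randomization paragraph that ends Section 3.1 makes allocation open: "the second group will not receive any treatment but will be followed up regularly". There is no placebo immunotherapy.

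Section 3.3.6 defines the primary outcome as tolerating 200 ml of milk one year after the start of the trial, and counts only total desensitization as success. The minimum dose that triggers symptoms is a secondary outcome.

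**The concern.** The challenge is the only placebo-controlled element that the plan describes, and its result feeds three things: eligibility (a negative entry challenge excludes the subject), the primary outcome, and the triggering dose. A placebo session guards against over- or under-reading of symptoms only if the person reading them does not know which session is which. If that person also knows the arm, a doubtful symptom can be called one way in a treated child and the other way in a control. Because success is all or nothing, one borderline call can decide a subject's primary result. The plan already has the parts needed for a masked reading, namely a placebo session, a randomized order and someone who prepares the drinks. It does not say that the order is kept from the scorer.

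**Working it through.** **1. Who knows what, from the text.**
- Patient: masked to the order (usual reading of single blind), aware of arm.
- Preparing nurses: know the order, because they set it.
- Scorer: not named; masking to order or arm not mentioned. Section 3.3.3 and Appendix C call later challenges blinded without adding detail.

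That the scorer knows the order is therefore an inference. That no masked scorer is specified is a fact.

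**2. Does the blinded series reach the endpoint?** The plan's stated total is 150 ml. The doses listed in Section 3.2 give 0.1 + 0.3 + 1 + 3 + 10 + 30 + 45 + 60 = 149.4 ml, which matches after rounding. This is below the 200 ml threshold in Section 3.3.6, and the confirmation step that follows is open.

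**3. Is a blinded challenge scheduled at one year in both arms?**
- Section 3.3.3 gives those who reach 200 ml a challenge with a maximum of 300 ml. It exceeds the threshold, but comes after one month at that dose, not at one year.
- Section 3.3.3 writes a 12-month blinded challenge only for subjects who tolerate less than 200 ml.
- The Control Subjects paragraph lists skin tests, blood tests and diaries. Section 5 implies a one-year control challenge, as a condition for later therapy.
- The Experimental Approach summary mentions a challenge after one year of therapy, without stating its blinding.
- Appendix C lists blinded challenges at Visit 2 and at Visit 24 (one month after OIT stops), and none at Visit 28.

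These places do not agree on when, how and in whom the endpoint is measured.

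**4. Size of one changed call.** With 42 subjects in the OIT arm (Section 4.0), 1/42 = 2.4 points, 2/42 = 4.8 points and 4/42 = 9.5 points. The documents give no basis for how many calls would change.

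**5. Illustration; every rate is assumed.** Suppose there is no true effect, true success is p in both arms, and a scorer who knows the arm turns a share b of OIT failures into successes and b of control successes into failures. Observed rates are then p + (1 − p)b for OIT and p(1 − b) for controls. With p = 0.10 and b = 0.10:
- OIT: 0.10 + 0.90 × 0.10 = 0.19. Control: 0.10 × 0.90 = 0.09. Pooled: 0.14.
- Expected changed calls: 42 × 0.90 × 0.10 = 3.8 in OIT and 42 × 0.10 × 0.10 = 0.4 in controls.
- SE under the null: √(2 × 0.14 × 0.86 / 42) = 0.0757. SE under the observed rates: √((0.19 × 0.81 + 0.09 × 0.91) / 42) = 0.0749.
- Chance of a significant result favouring OIT: Φ((0.10 − 1.96 × 0.0757) / 0.0749) = Φ(−0.646) = 0.26, against a nominal 0.025.

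| True success p | b = 5% | b = 10% | b = 20% |
|---|---|---|---|
| 10% | 0.10 | 0.26 | 0.67 |
| 20% | 0.08 | 0.19 | 0.55 |

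The two-sided comparison of proportions at 0.05 is also an assumption, since Section 4.0 names only t-tests and regression. The table describes knowledge of arm, which hiding the order does not remove. It shows that few calls matter at this sample size; it does not measure the gain from the fix.

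**The case against.** The strongest reply is that the harm needs knowledge of arm, whereas hiding the order conceals only the substance. Knowing which drink is milk is not in itself differential between arms, and a scorer who knows that a child had OIT can be lenient in both sessions. This largely stands. A hidden order mainly restrains over-calling, because a scorer who calls too freely will also call placebo sessions positive. Leniency in both sessions leaves no such trace. Hence the scorer should, where possible, also not be told the arm.

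Second, Section 3.2 restricts scoring to objective symptoms, and signs such as urticaria, angioedema and wheeze can be observed. That is a real safeguard and limits the number of doubtful calls. It does not remove them, because the same paragraph admits a single symptom and protracted abdominal pain.

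Third, the rationale in Section 2.2 that "there are few rigorous, blinded clinical trials, with adequate controls and outcomes" describes earlier trials. It does not commit this one to double-blind challenges, and the point does not rest on it.

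A reader might also infer that scorers certainly know both order and arm, or that the change needs no extra person. The documents support neither. The scorer is unnamed, the same nurses might prepare and score, and recruitment covers three centres.

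**Conclusion.** The point holds as a gap that is cheap to close. The challenges are single blind in an open-label trial, and the plan specifies no scorer masked to the milk/placebo order or to arm. That the observer is the unblinded party is an assumption from usual usage. The size is 2.4 points of OIT success per changed call, with the number of such calls unknown.

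It is tempting to conclude that concealing the order would make the primary outcome double-blind. The documents do not support that. The blinded series ends below 200 ml, its confirmation is open, and no blinded one-year challenge is clearly scheduled for subjects who reached 200 ml or for controls. Arm may also remain known.

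**What to change.** In Section 3.2, make the baseline and follow-up challenges double-blind:

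- The nurse who prepares the food keeps the order, in a code that can be opened at once for safety.
- A different member of the existing medical or nursing staff, where possible one not told the arm, records the result of both sessions before the order is revealed.
- The plan names the scorer's role and states who is masked to what.

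The cost is mainly a change to the challenge procedure. Preparer and scorer must be different people, which each centre would have to confirm. The two drinks must look alike to the observer as well as to the patient; Section 3.2 describes no masking method. Sample size, alpha and power do not change, and protection stays partial wherever arm is known.

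Separately, reconcile Sections 3.2, 3.3.3, 3.3.6 and 5, the Control Subjects paragraph and Appendix C on challenge volume and timing, so that a blinded challenge covers the 200 ml one-year endpoint in both arms. No dose or schedule is proposed here; that is for the investigators to settle.

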3.3.3 Maintenance phase

Patients who reach the maintenance dose of 200 ml will be instructed to continue and consume 200 ml of milk daily for 1 month. They will then undergo an oral challenge (see above), with the maximum dose of 300ml.

If this 300 ml dose is tolerated, they will be permitted to consume dairy products without restrictions and attend regular follow up visits for 12 months. It will be recommended to consume dairy at least twice weekly, if not more, to maintain the desensitization.

Subjects who tolerate less than the 200 ml upper dose will be instructed to continue their maximum tolerated dose for the 12 month follow-up period, at which time another blinded milk challenge will be performed to determine if their tolerance increased.

3.3.4 Long Term Follow-up: to assess the persistence of milk desensitization from clinical, cellular and molecular perspectives, participants will be asked to return to the research center once a year for five years following the end of the Maintenance Phase. At these visits, participants will be asked about their dairy consumption, any reactions they may have experienced in the interval between the last visit and changes in their quality of life (as assessed by questionnaire). Participants will also have the following analyses done: SPT, salivary IgA, serum milk-specific IgE, IgA and IgG4 concentrations, Glycosylation state, Vitamin D levels, and B and T cell regulatory cell phenotyping. Participants will be reminded of the importance of continuing the consumption of dairy products in the maintenance of desensitization. Participants who have completed the study will be asked to reconsent to the extension. Given that these participants may not have scheduled visits to the hospital, to lessen their inconvenience, a delegated member of the study team might make a home visit in order to obtain informed consent

3.3.4 Control Subjects: Subjects randomized to no treatment will be followed every 3-6 months as is standard in our clinic for milk allergy. They will have skin testing and blood testing as on routine follow-ups, but they will be required to fill out symptoms diaries. At the end of the study period, oral desensitization will be offered to the control patients who had not spontaneously achieved tolerance.

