Withdrawal from therapy: Subjects will be carefully monitored during the in hospital rush therapy phase, as well as during the home OIT phase. Instructions for treatment of reactions will be provided as above. Patients who are enrolled will be informed that in previously published studies, minor allergic reactions are common in these protocols (mild itching, abdominal discomfort) but resolve with increased time on therapy. Subjects will be withdrawn if they cannot tolerate the low dose, rush desensitization phase, if they have more than 2 or more moderate or severe reactions during the home (maintenance) OIT phase, if they experience a rare or unforeseen complication such as severe flares of eczema or chronic gastrointestinal symptoms (e.g. development of eosinophilic esophagitis) and if the parents or subjects wish to voluntarily terminate therapy.

3.3.6 : Variables measured. The following variables will be measured in each patient:

A. The primary outcome measure will be the presence of desensitization defined by the ability to tolerate 200 ml of milk 1 year after the start of the trial. This is a qualitative variable with three categories: total desensitization (200 mL of cow's milk); partial desensitization (20–200 mL); and failed desensitization (<20 mL milk). Only patients presenting total desensitization were regarded as being successfully desensitized.

B. Secondary outcome measures will be:

1. Number and severity of adverse reactions occurring after oral exposure to milk during the desensitization and follow-up phases.
2. Minimum dose of milk that triggered symptoms during the desensitization protocols or challenge tests.
3. Days until desensitization was achieved.
4. Indices of desensitization :
 - a. Change in skin prick test weal size, comparing tape transferred, cpoputor measured diameters and areas of the skin tests to milk extract.
 - b. Levels of sIgE, sIgA and sIgG4 before desensitization, during follow-up and at the end of the study.
 - c. T and B reg before desensitization, during follow-up and at the end of the study.

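### The only written milk-challenge ladder ends at about 150 ml, so by milk volume it cannot show the primary endpoint of tolerating 200 ml at 1 year, and the two arms may be judged against different ceilings.

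*Combined protocol and SAP*

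**What the plan says.** **The challenge (section 3.2).** "Prior to initiating desensitization and following treatment, the subjects will undergo a placebo controlled oral challenge to milk". Eight doses are listed (0.1, 0.3, 1, 3, 10, 30, 45 and 60 ml), given "with increasing doses taken orally every 10 to 15 minutes up to a total of 150ml of milk". If that part is negative, "results will be confirmed by means of open challenge, using 250ml of yogurt or ice cream". At baseline a negative result ends participation: if "the subject is asymptomatic, he/she will be excluded from the study".

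**The endpoint (section 3.3.6 A).** The primary outcome is "the ability to tolerate 200 ml of milk 1 year after the start of the trial". It has three categories: total (200 mL of cow's milk), partial (20–200 mL) and failed (under 20 mL). "Only patients presenting total desensitization were regarded as being successfully desensitized".

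**Other challenges after treatment starts.**
- Section 3.3.3, immunotherapy subjects who have taken 200 ml daily for one month: "They will then undergo an oral challenge (see above), with the maximum dose of 300ml".
- Section 3.3.3, immunotherapy subjects below 200 ml, at the end of the 12-month follow-up: "another blinded milk challenge will be performed to determine if their tolerance increased". No maximum is given.
- Section 5, controls: a positive challenge after a year of observation is required before they may have therapy. No maximum is given.
- The Experimental Approach summary calls for a challenge after one year of therapy. No maximum is given.
- Appendix C lists blinded challenges at Visit 2 and Visit 24 only.

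**The concern.** The challenge is the tool that measures tolerance, and the only version with written doses stops below the volume that defines success. No sentence says how passing the blinded part, with or without the open yogurt or ice cream step, maps to the three categories of section 3.3.6.

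The gap does not fall evenly. Immunotherapy subjects at 200 ml have a written challenge that goes past the threshold, though not at 1 year. Controls and lower-dose immunotherapy subjects have none with a stated maximum. If their challenge follows the section 3.2 ladder and is scored by millilitres of milk, the best they can record is partial, which counts as non-success. The same negative result at baseline would have excluded them as not allergic. At stake is whether the primary comparison measures both arms against the same ceiling. In an unmasked trial with an untreated control group, there is also the risk that scoring is settled after results are known.

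**Working it through.** **Inputs.** Challenge doses and stated total: section 3.2. Threshold and categories: section 3.3.6. Dose timetable: Appendix B. Arm size of 42: section 4.0.

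**1. The plan's own total.** 0.1 + 0.3 + 1 + 3 + 10 + 30 + 45 + 60 = 149.4 ml, against the stated 150 ml. The 0.6 ml difference is rounding and not an issue.

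**2. Each step against the section 3.3.6 categories.**

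| Dose (ml) | Cumulative (ml) | Category by milk volume |
|---|---|---|
| 0.1 | 0.1 | failed |
| 0.3 | 0.4 | failed |
| 1 | 1.4 | failed |
| 3 | 4.4 | failed |
| 10 | 14.4 | failed |
| 30 | 44.4 | partial |
| 45 | 89.4 | partial |
| 60 | 149.4 | partial |

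No step reaches total. Shortfall: 200 − 149.4 = 50.6 ml; 50.6 / 200 = 25.3%. The largest single dose is 60 ml.

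**3. Timing of the 300 ml challenge.** Appendix B reaches 200 ml at Week 17. Adding one month (about 4 weeks) gives about Week 21, not 1 year.

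**4. Who has a written challenge past 200 ml.**

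| Group | Challenge | Stated maximum |
|---|---|---|
| Immunotherapy, at 200 ml | about Week 21 | 300 ml |
| Immunotherapy, below 200 ml | 12 months | none |
| Controls | after one year | none |

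**5. Effect on the difference.** With 42 per arm, one reclassified subject is 1/42 = 2.4 points. If *k* tolerant controls and *m* tolerant lower-dose immunotherapy subjects are scored partial instead of total, the reported difference is off by (*k* − *m*)/42: too large if *k* > *m*, too small if *k* < *m*, unchanged if equal. The documents give neither number.

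**6. Illustration of the control side only.** Assume *m* = 0 and *k* from 0 to 5 (an assumption; the documents give no 1-year tolerance rate for enrolled subjects). Two illustrative success counts are used for immunotherapy, with two-sided Fisher tests.

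| Immunotherapy successes | Control successes | Difference (points) | p |
|---|---|---|---|
| 21/42 | 0/42 | 50.0 | 3.3e-8 |
| 21/42 | 5/42 | 38.1 | 0.0003 |
| 15/42 | 0/42 | 35.7 | 1.3e-5 |
| 15/42 | 5/42 | 23.8 | 0.020 |

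The estimate moves by up to 5/42 = 11.9 points, and p stays below 0.05 throughout. This bounds one of two opposing errors under an assumed count; it does not estimate the net bias.

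**7. What an extension would reach.** One further 60 ml step: 149.4 + 60 = 209.4 ml. A further 90 ml step: 209.4 + 90 = 299.4 ml, in effect the 300 ml maximum.

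**The case against.** **Partial scoring is only one reading.** Section 3.3.6 classifies by ability to tolerate milk. A subject who passes 150 ml and then 250 ml of yogurt or ice cream has shown no limit between 20 and 200 ml, and the plan treats a negative challenge as tolerance elsewhere. This is a fair point: a sensible assessor might well score such a subject as total. But section 3.3.6 specifies cow's milk in millilitres, and no milk equivalent is given for the open step, so two assessors could differ.

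**The ceiling may already be 300 ml.** Section 3.3.3 raises the maximum, then speaks of another blinded challenge for lower-dose subjects, which could mean the same version. That is possible, so the point about lower-dose subjects is conditional on the section 3.2 ladder being used. It does not help controls.

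**The arms may not really differ.** A reader might infer that immunotherapy subjects on 200 ml are automatically counted as successes while controls cannot be. The documents do not support this. Section 3.3.6 never says that the home dose or the Week 21 challenge supplies the 1-year result. What stands is that the 1-year measurement is unspecified in both arms and that only one subgroup has a written challenge past the threshold.

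**The number affected is probably small.** A misclassified control must react at baseline, go untreated, and then pass everything a year later. This stands, and it limits the size of the point.

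**Conclusion.** The point holds and should be fixed. The only challenge with written doses cannot show the primary endpoint by milk volume, and the challenges at about 1 year for controls and lower-dose immunotherapy subjects have no stated maximum. The arithmetic and the missing scoring rule are certain. The bias is conditional: it needs the section 3.2 ladder at 1 year, scoring by milk volume, and at least one subject who passes the full challenge.

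A reader might infer that the treatment effect is inflated, by as much as 11.9 points. The documents do not support that. The figure rests on an assumed 0 to 5 of 42 controls and ignores the opposite error in lower-dose immunotherapy subjects. Net size and direction are unknown and probably small. The point bears on the estimate; it is unlikely to change whether a large effect is detected. The sample size is unaffected.

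**What to change.** **Preferred.** Leave the baseline challenge in section 3.2 unchanged, so that eligibility stays the same. Run the 1-year challenge that the Experimental Approach and section 5 already imply, in both arms and whatever the home dose, to the same 300 ml maximum used in section 3.3.3 (for example, further steps of 60 and 90 ml). At the least, add one 60 ml step (209.4 ml cumulative). State in section 3.3.6 that the category is the cumulative milk tolerated on that challenge, and that the Week 21 challenge does not supply it. List the 1-year challenge for both arms in Appendix C.

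**Fallback, if the clinical team will not extend the ladder.** State in section 3.3.6 that passing 150 ml plus the open 250 ml step counts as total desensitization in both arms. This adds no milk, but it only settles the scoring: 200 ml of milk itself is still not tested.

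**Cost.** The text changes are one sentence in section 3.3.6, one follow-up-only line in section 3.2 and one Appendix C entry. Under the preferred option, those who pass 150 ml take 60 to 150 ml more milk over about 10 to 30 more minutes (one or two steps at 10 to 15 minutes), with some added chance of a reaction. Any subject for whom no 1-year challenge was planned needs one challenge day. Section 3.3.3 writes only follow-up visits for those who pass 300 ml, so this group may include them; the documents do not allow a count.

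### Section 3.2 promises a single-blind milk challenge but names two different drinks, one of each per day, with no common masking vehicle and no named blinded party

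*Combined protocol and SAP*

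**What the plan says.** Section 3.2 (Oral challenge test to milk) makes these statements:

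- On blinding and the active drink: "Oral challenges will be single blinded and will be performed with fresh cow's milk".
- On the placebo: "Unless contraindicated, the placebo will be soy or rice-based milk".
- On the day's content: "Patients will receive 2 challenges per day, 1 placebo and 1 with the active substance (milk").
- On preparation, the unit nurses "will prepare the food and randomize the placebo challenges".
- On scoring: "Only objective symptoms will be considered to be indicative of a positive allergic reaction (29"). The next sentence reads "Food challenges will be scored as positive if a single symptom or any of the following objective clinical reactions will be observed", and the list that follows ends with "protracted abdominal pain, exacerbation of atopic dermatitis, or shock". A negative result is then equated with a child who has no symptoms.

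Section 3.3.3 (Maintenance phase) has children who reach the top dose "consume 200 ml of milk daily for 1 month" and then take a challenge of the kind set out in 3.2, up to 300 ml. Children who stop below 200 ml have another blinded challenge at 12 months. Appendix C lists a blinded, placebo-controlled challenge at Visits 2 and 24.

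**The concern.** A single blind works only if the blinded person cannot tell the two preparations apart. Cow's milk and a soy or rice drink are different products, and 3.2 describes nothing that makes them look or taste alike. It does not say who is blinded, and it collects nothing that would show whether the blind held.

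A negative challenge at entry excludes the child. The reaction level at entry is the baseline. The Experimental Approach makes the amount of milk safely consumed on challenge, before and after OIT, the primary clinical outcome. Treatment allocation is open, so the challenge blind is the only masking described for a clinical outcome. If it is weak, the placebo session gives less protection than intended against symptoms reported because the child expects them.

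**Working it through.** The plan gives no figure for this point, so there is none to reproduce. The check has four steps.

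**1. Does recognising one session reveal the other?** From 3.2, the day holds exactly one milk and one placebo session in random order. Identifying either therefore identifies both. Let r be the share of children who recognise milk, and let the rest guess the order correctly half the time. The share who identify both sessions is then r + (1 − r)/2:

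| r (assumed) | r + (1 − r)/2 |
|---|---|
| 0 | 0.50 |
| 0.25 | 0.25 + 0.375 = 0.625 |
| 0.50 | 0.50 + 0.25 = 0.75 |
| 0.75 | 0.75 + 0.125 = 0.875 |
| 1 | 1.00 |

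The documents give no value of r, so the table shows a range and not an estimate. It also leaves out anything a child learns from having a reaction.

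**2. When is recognition plausible?** At baseline the children avoid milk and the first three steps in 3.2 are 0.1, 0.3 and 1.0 ml, so recognition there is uncertain. The later steps are 10, 30, 45 and 60 ml. At follow-up, a child who reached maintenance has taken 200 ml of milk a day for a month (3.3.3). That such a child would recognise milk at the larger steps is an inference, but a strong one.

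**3. Could recognition change a score?** Three statements in 3.2 sit side by side:

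- Only objective symptoms count.
- A challenge is positive on a single symptom or on any listed reaction, and the list includes prolonged abdominal pain, which depends on what the child reports.
- A negative challenge means no symptoms.

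The first statement closes the door on reported symptoms. The other two leave it partly open.

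**4. What rests on the result?** Entry and the baseline reaction level (3.2), and the before/after tolerated amount (Experimental Approach). Section 3.3.6 defines desensitization by tolerance of 200 ml at one year without saying how tolerance is tested.

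**The case against.** The strongest reply is that silence about preparation does not show that masking is absent. The nurses prepare the food, 3.2 cites published challenge methods, and a working blind may be routine in the unit. One active and one placebo session in random order is also an ordinary placebo-controlled design, so the pairing itself is not a defect. The objective-symptom rule governs scoring, and the abdominal pain must be prolonged to count. A negative blinded challenge is in any case confirmed by an open one with yogurt or ice cream.

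Much of this stands. The documents do not show that children can tell the drinks apart, so it would be wrong to say that the blind fails. What remains is that 3.2 names two different drinks and claims a blind that those drinks, given as described, are unlikely to deliver to a child who drinks milk every day. The open confirmation applies only after a negative result. It does not correct a challenge stopped early or scored positive.

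A reader might also infer that the bias favours OIT, because untreated children would be more apprehensive about milk. The documents do not support that:

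- Section 3.3.4 (Control Subjects) lists skin tests, blood tests and diaries, but no blinded challenge. Section 5 mentions a positive challenge after a year without saying that it is blinded.
- On a success/failure outcome, the loss in an arm is its true success rate times its false-stop rate. If the false-stop rate were the same in both arms, the arm with the higher success rate would lose more. With an assumed rate of 5%, the loss is 0.60 × 0.05 = 3.0 points at 60% success and 0.05 × 0.05 = 0.25 points at 5% success, which works against OIT. The opposite direction needs more false stops in controls, and nothing in the documents shows this.
- Some false stops would occur under good masking too. Only the difference between masked and unmasked rates is due to the blind, and the documents give neither.

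**Conclusion.** The point holds in a limited form. Section 3.2 claims a single blind without a described means of achieving it and without naming who is blinded, and recognising one session reveals both. The weakness is most plausible at follow-up in OIT children and uncertain at the smallest baseline doses. The scoring text leaves some room for expectation despite the objective-symptom rule.

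Neither the size nor the direction of any effect on results can be derived from the documents. The conclusion assumes that the challenge is run with the drinks as named and that daily milk drinkers can often recognise milk. It does not assume that every child can. The plan should be amended because the change is cheap and concerns a test on which entry and a main outcome rest.

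**What to change.** Amend 3.2 as follows:

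- The same nurses give milk and placebo in one common vehicle, matched for volume, colour and flavour at each step, with the milk doses unchanged.
- The text states that the child is the blinded party.
- Each session's score is locked before the next session starts and before the order is opened.
- After each session the child is asked which drink it was, and the share of correct guesses is reported beside the challenge results as a check on the blind.

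No extra patients or visits are needed. The costs are slightly larger drink volumes, masking that may be imperfect at the 45 and 60 ml steps, and the need for a vehicle that suits each child's other allergies. The protocol is marked as revised in July 2018, and the long-term follow-up section refers to participants who have completed the study, so some children have probably already had their baseline challenge. For them a new vehicle would differ between baseline and follow-up. The change should therefore apply to newly enrolled children, or the vehicle used at each challenge should be reported.
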